**Yes**

→ If yes, explain whether and how you would share the information with the subject.

b. Do you plan to share the individual results of any of your study procedures or findings with the subjects – such as genetic test results, laboratory tests, etc.?

**No****Yes**

→ If yes, complete and upload the [**SUPPLEMENT: Participant Results Sharing**](#) to the **Supporting Documents** SmartForm of **Zipline**

10.10 Commercial products or patents. Is it possible that a commercial product or patent could result from this study?

**No****Yes**

→ If yes, describe whether subjects might receive any remuneration/compensation and, if yes, how the amount will be determined.

11 ECONOMIC BURDEN TO PARTICIPANTS

11.1 Financial responsibility for research-related injuries. Answer this question only if the lead researcher is not a UW student, staff member, or faculty member whose primary paid appointment is at the UW.

Describe who will be financially responsible for research-related injuries experienced by subjects, and any limitations. Describe the process (if any) by which participants may obtain treatment/compensation.

11.2 Costs to subjects. Describe any research-related costs for which subjects and/or their health insurance may be responsible (examples might include: CT scan required for research eligibility screening; co-pays; surgical costs when a subject is randomized to a specific procedure; cost of a device; travel and parking expenses that will not be reimbursed).

11.3 Reimbursement for costs. Describe any costs to subjects that will be reimbursed (such as travel expenses).

12 RESOURCES

12.1 Faculty Advisor. (For researchers who are students, fellows, or post-docs.) Provide the following information about your faculty advisor.

- Advisor's name
- Your relationship with your advisor (for example: graduate advisor; course instructor)
- Your plans for communication/consultation with your advisor about progress, problems, and changes.

N/A

12.2 Study team communication. Describe how you will ensure that each study team member is adequately trained and informed about the research procedures and requirements (including any changes) as well as their research-related duties and functions.

There is no study team.

The PI will train the study team on the study procedures. The study physiotherapist will be certified in the use of personalized blood flow restriction training.

13 OTHER APPROVALS, PERMISSIONS, and REGULATORY ISSUES

13.1 Other regulatory approvals. Identify any other regulatory approvals that are required for this research, by checking applicable boxes

Do not attach the approvals unless requested by the IRB.

Approval	Research for which this is required
 Radiation Safety	Procedures involving the use of radioactive materials or an ionizing radiation producing machine radiation, if they are conducted for research rather than clinical purposes. Approvals need to be attached to the Supporting Documents page in Zipline .
 Institutional Biosafety	Procedures involving the transfer/administration of recombinant DNA, DNA/RNA derived from recombinant DNA, or synthetic DNA.
 RDRC	Procedures involving a radioactive drug or biological product that is not approved by the FDA for the research purpose and that is being used without an IND, for basic science research (not to determine safety and effectiveness, or for immediate therapeutic or diagnostic purposes).
 ESCRO	Procedures involving the use of some types of human embryonic stem cells.

13.2 Approvals and permissions. Identify any other approvals or permissions that will be obtained. For example: from a school, external site/organization, funding agency, employee union, UW Medicine clinical unit.

Do not attach the approvals and permissions unless requested by the IRB.

13.3 Financial Conflict of Interest. Does any member of the team have a Financial Conflict of Interest (FCOI) in this research, as defined by [UW policy GIM 10?](#)

No

Yes → If yes, upload the Conflict Management Plan for every team member who has a FCOI with respect to this research, to the **Supporting Documents** page of **Zipline**. If it is not yet available, use the text box to describe whether the Significant Financial Interest has been disclosed already to the UW Office of Research.

NCT04635579

Personalized Blood Flow Restriction for Anterior Cruciate Ligament Rehabilitation

04/24/2018

Statistical Analysis

For the biomechanical variables, two primary sets of statistical comparisons were performed. First, the healthy and anterior cruciate ligament reconstruction (ACLR) group were compared to each other for the final set of step-ups during both the control and personalized blood flow restriction (PBFR) exercise conditions. Then, both groups were compared between the control and PBFR conditions for the same timepoint (repeated measures). Statistical parametric mapping a technique which allows the temporal data such as that collected during this type of biomechanical study to be compared, was used to test for statistically significant differences between the kinematic and kinetic waveforms. This approach allowed the full dataset to be compared, rather than looking at discrete values such as the peak range of motion. The significance level was adjusted to $\alpha = 0.001$ to account for multiple comparisons. Descriptive statistics were calculated for the peak movement for all motions. Participant reported scores for difficulty and discomfort were compared using Wilcoxon signed-rank tests (between exercise conditions) and Wilcoxon rank-sum tests (within exercise conditions). Data were analyzed using R V3.5.2 and Python 2.7. Figures were produced using the ggplot2 package.

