HSD may ask for documentation of the externally-imposed urgency. A higher priority should not be requested to compensate for a researcher's failure to prepare an IRB application in a timely manner. Note that IRB review requires a certain minimum amount of time; without sufficient time, the IRB may not be able to review and approve an application by a deadline.

	No
	Yes

→ If yes, briefly describe the urgency or deadline as well as the reason for it.

1.5 Objectives Using lay language, describe the purpose, specific aims, or objectives that will be met by this specific project. If hypotheses are being tested, describe them. You will be asked to describe the specific procedures in a later section.

If your application involves the use of a HUD “humanitarian” device: describe whether the use is for “on-label” clinical patient care, “off-label” clinical patient care, and/or research (collecting safety and/or effectiveness data).

Specific Aims

Aim 1: To determine the acceptability of personalized blood flow restriction training during free standing exercises for individuals undergoing rehabilitation for anterior cruciate ligament reconstruction

Aim 2: To determine if personalized blood flow restriction training affects stability and control while performing free standing exercises

Hypotheses

H1: BFR during free standing exercises will be acceptable to individuals undergoing rehabilitation after ACL reconstruction surgery; and H2: While performing exercises with BFR, participants will be less stable compared to the no BFR condition. In addition, we will test a secondary hypothesis, H3: varying the level of restriction will induce a “dose-response” effect in the biomechanical variables of interest.

1.6 Study design. Provide a one-sentence description of the general study design and/or type of methodology.

Your answer will help HSD in assigning applications to reviewers and in managing workload. Examples: a longitudinal observational study; a double-blind, placebo-controlled randomized study; ethnographic interviews; web scraping from a convenience sample of blogs; medical record review; coordinating center for a multi-site study.

This is a cross-sectional study on the use of personalized blood flow restriction during rehabilitation exercises and its effects on biomechanics

1.7 Intent. Check all the descriptors that apply to your activity. You must place an "X" in at least one box.

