This question is essential for ensuring that your application is correctly reviewed. Please read each option carefully.

Descriptor
 1. Class project or other activity whose purpose is to provide an educational experience for the researcher (for example, to learn about the process or methods of doing research).
 2. Part of an institution, organization, or program's own internal operational monitoring.
 3. Improve the quality of service provided by a specific institution, organization, or program.
 4. Designed to expand the knowledge base of a scientific discipline or other scholarly field of study, and produce results that: 
• Are expected to be applicable to a larger population beyond the site of data collection or the specific subjects studied, or• Are intended to be used to develop, test, or support theories, principles, and statements of relationships, or to inform policy beyond the study.
 5. Focus directly on the specific individuals about whom the information or biospecimens are collected through oral history, journalism, biography, or historical scholarship activities, to provide an accurate and evidence-based portrayal of the individuals.
 6. A quality improvement or program improvement activity conducted to improve the implementation (delivery or quality) of an accepted practice, or to collect data about the implementation of the practice for clinical, practical, or administrative purposes. This does not include the evaluation of the efficacy of different accepted practices, or a comparison of their efficacy.
 7. Public health surveillance activities conducted, requested, or authorized by a public health authority for the sole purpose of identifying or investigating potential public health signals or timely awareness and priority setting during a situation that threatens public health.
 8. Preliminary, exploratory, or research development activities (such as pilot and feasibility studies, or reliability/validation testing of a questionnaire)
 9. Expanded access use of a drug or device not yet approved for this purpose
 10. Use of a Humanitarian Use Device

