Guided by an experienced physiotherapist and after a short warm-up, the participant will be asked to perform a series of exercises using their injured leg in the case of the ACL group, or randomly chosen for the controls. The exercise is step up and step down from a 30cm high step. Each exercise will be performed 30 times, then a 30 second break followed by 3 sets of 15 repetitions with a 30 second break. This is the standard protocol for these rehabilitation exercises. Up to four conditions will be tested: 1) no BFR; 2) 80% LOP; 2) 60% LOP; 3) 40% LOP. The order of conditions will be randomized between participants. After each exercise is complete, participants will be asked to rate the difficulty and discomfort associated with performing each exercise on numerical analogue scales (0 – no difficulty/discomfort; 10: extremely difficult/uncomfortable). Participants will be given as much rest as needed between exercises.

The visit will not replace one of the participants standard rehab visits but participation in the study will be noted in the participant's medical record.

5.2 Data variables. Describe the specific data you will obtain (including a description of the most sensitive items). If you would prefer, you may upload a list of the data variables to the **Supporting Documents** SmartForm instead of describing the variables below.

Kinematic and kinetic variables from the motion capture system; muscle activity; date of birth, weight, height, sex, time since injury,

5.3 Data sources. For all types of data that you will access or collect for this research: Identify whether you are obtaining the data from the subjects (or subjects' specimens) or whether you are obtaining the data from some other source (and identify the source).

If you have already provided this information in Question 5.1, you do not need to repeat the information here.

All data will be collected from the subject.

5.4 Retrospective/prospective. For all types of data and specimens that you will access or collect for this research: do all data and specimens to be used in the research exist (for example, in subjects' medical records) at the time this application is being submitted for initial review?

	No
	Yes

Include any necessary comments or explanation below (Note that for most studies this can be left blank):

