There are written policies and procedures for the repository/database/data management center that prohibit the release of the identifiers (or identifying link). This includes situations involving an Honest Broker.

There are other legal requirements prohibiting the release of the identifiers or key to you. Describe them below.

b. Will you obtain any direct or indirect identifiers?

→ If yes, describe which identifiers and for which data/specimens.

Names and medical record numbers and email and/or phone number for contact

→ If no, select the reason(s) why you (and all members of your team) will not obtain direct or indirect identifiers.

There will be no identifiers.

Identifiers or the key have been (or will have been) destroyed before you have access.

You have (or will have) entered into an agreement with the holder of the identifiers (or key) that prohibits the release of the identifiers (or key) to you under any circumstances.

You should be able to produce this agreement for IRB upon request. Examples: a Data Use Agreement, Repository Gatekeeping form, or documented email.

There are written policies and procedures for the repository/database/data management center that prohibit the release of the identifiers (or identifying link). This includes situations involving an Honest Broker.

There are other legal requirements prohibiting the release of the identifiers or key to you. Describe them below.

c. If you obtain any identifiers, indicate how the identifiers will be stored (and for which data). NOTE: Do not describe your data security plan here – we will ask for that information in section 9.6.

You will store the identifiers with the data. Describe the data to which this applies:

You will store identifiers and study data separately but you will maintain a link between the identifiers and the study data (for example, through the use of a code). Describe the data to which this applies:

Upon enrollment into the study, the participant will be assigned a unique identifier of the form "PBFRxxx" where "xxx" are sequential numbers 001, 002, ... 030. Data identified using these IDs will be stored separately from any personal information that could identify the individual. All de-identified data will be stored on password protected computers in the Computational, Robotic, and Experimental Biomechanics laboratory. Names and contact details will be kept separately in a locked filing cabinet, room BB1002.

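### The SAP compares only control with PBFR, does not say which LOP level or levels PBFR means, and contains no analysis of the protocol's secondary dose-response hypothesis H3

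*SAP*

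**What the plan says.** Protocol section 1.5 (Objectives) lists H1 (acceptability) and H2 (less stability with BFR than without), then adds: "In addition, we will test a secondary hypothesis, H3: varying the level of restriction will induce a" dose-response effect in the biomechanical variables.

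Protocol section 5.1 (Study procedures) supplies the conditions: "Up to four conditions will be tested: 1) no BFR; 2) 80% LOP; 2) 60% LOP; 3) 40% LOP". On sequence it says: "The order of conditions will be randomized between participants".

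The SAP's Statistical Analysis text describes two primary sets of biomechanical comparisons, both on the final set of step-ups. The first compares healthy with ACLR participants "during both the control and personalized blood flow restriction (PBFR) exercise conditions". The second is within participants: "Then, both groups were compared between the control and PBFR conditions for the same timepoint (repeated measures". The method is statistical parametric mapping (SPM) of waveforms, with alpha set to 0.001 "to account for multiple comparisons". The number of comparisons behind that figure is not given.

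The SAP mentions no LOP value, ordered contrast or restriction-level factor, and does not mention H3.

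**The concern.** A comparison of cuff with no cuff can address H2. It cannot address H3, because one non-zero condition set against zero does not separate an effect that grows with restriction from one that is the same at any restriction. A reader who follows the SAP exactly reaches the end with a stated secondary hypothesis neither tested nor withdrawn.

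The undefined label also reaches the primary analysis. PBFR could be the only level run, one level chosen from several, a pool of levels, or each level in turn. These are different estimands and imply different numbers of tests. If it is one level, the results apply to that level only, and the SAP does not identify it.

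**Working it through.** **Step 1. The texts side by side.**

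| Item | Protocol | SAP |
|---|---|---|
| Exercise conditions | Up to 4: none, 40%, 60%, 80% LOP (5.1) | 2: control, PBFR |
| Non-zero levels | Up to 3 | Not stated |
| Contrasts available or named | 6 pairwise among 4 conditions (4 × 3 / 2), 3 of them against no BFR | 1: control versus PBFR |
| Dose-response in biomechanics | To be tested as H3 (1.5) | No level term, no trend, no statement that it was dropped |

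The SAP's signed-rank tests between exercise conditions do not fill the gap. They are paired two-condition tests of difficulty and discomfort scores, whereas H3 concerns biomechanics. The protocol as supplied has no statistical section that covers H3.

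Neither document gives a power figure, effect size, SD or within-person correlation, so there is no planned figure to reproduce. The remaining steps show only what an added analysis could deliver. Their inputs are assumptions, and the gap in the text does not depend on them.

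**Step 2. Precision among the non-zero levels.** Assume a single scalar outcome and means linear in LOP: 0, 0.5D, 0.75D and D at 0, 40, 60 and 80%. Let sigma be the between-person SD within a condition and rho the within-person correlation; take D = 1 sigma. For equally spaced 40/60/80% the linear trend reduces to the 80%-minus-40% difference:

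- mean 0.5D, SD sigma × sqrt(2(1 − rho));
- noncentrality = 0.5 / sqrt(2(1 − rho)) × sqrt(n).

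For n = 30 and rho = 0.5 this is 0.5 / 1 × 5.477 = 2.74, against two-sided critical values (29 df) of 2.05 at alpha 0.05 and 3.66 at alpha 0.001. Power is 75% and 21%. If only two adjacent levels were run, the mean difference is 0.25D, the noncentrality 1.37, and power 26% and 2%.

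Range over the assumed correlation, trend across 40/60/80%, D = 1 sigma:

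| rho | n = 30, alpha 0.05 / 0.001 | n = 15, alpha 0.05 / 0.001 |
|---|---|---|
| 0 | 46% / 6% | 25% / 1.5% |
| 0.5 | 75% / 21% | 44% / 4.5% |
| 0.8 | 99% / 74% | 81% / 21% |

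The n = 30 column uses the maximum per group in protocol section 2.7. The n = 15 column applies if the identifiers in section 5.5, which "are sequential numbers 001, 002, ... 030", cover both groups equally.

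**Step 3. Why the role of 0% must be stated.** A linear contrast over 0/40/60/80% has weights −45, −5, 15, 35 (sum of squares 3,500) and SD sigma × sqrt(3,500 × (1 − rho)) = 41.83 sigma at rho = 0.5.

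- Linear means with D = 1: −2.5 + 11.25 + 35 = 43.75. Noncentrality 43.75 / 41.83 × 5.477 = 5.73, so power is 97% at alpha 0.001, against 21% without 0%.
- Flat cuff effect of 0.5 sigma at every level: −2.5 + 7.5 + 17.5 = 22.5. Noncentrality 2.95, so the same contrast is significant in 81% of studies at alpha 0.05 and 27% at 0.001, although nothing changes between levels.

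Including 0% therefore gains power if the response is linear, but also picks up a flat effect. Excluding it has the opposite properties and would largely miss a saturating response: with assumed means 0, 0.8, 0.95, 1.0 and rho = 0.5, the 40/60/80% trend has 19% power at alpha 0.05 and 1% at 0.001.

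**The case against.** The strongest defence is that the protocol permits what the SAP describes. Section 5.1 says up to four conditions, so control plus a single level is within protocol, and H3 would then be untestable by design. H3 is secondary, and section 1.7 ticks only "Preliminary, exploratory, or research development activities". The SAP describes its comparisons as primary, so silence about a secondary analysis is an omission, not a contradiction. All of this stands, and it limits the severity. It does not supply the missing level, and it does not tell the reader what became of H3. If only one level was run, naming it matters more.

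A reader might go further and infer that all three levels were run and that the dose-response results were left out, or that one level was picked after the data were seen. The documents do not support that. The cap on cuff time in section 10.1 (20 minutes in 6 to 7 minute intervals; 20/7 = 2.9 to 20/6 = 3.3 intervals) is consistent with three inflated conditions, but does not show that three were run. Nothing describes how a level was selected.

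It is also tempting to say that H3 must be tested without 0%. H3 speaks of varying the level and does not exclude zero, and step 3 shows costs both ways. That choice belongs to the sponsor.

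**Conclusion.** The point holds on the text, at moderate severity. The SAP as written cannot answer H3, and its primary within-participant contrast, like the PBFR half of the between-group comparison, refers to a level or levels that it does not identify. The size that rests on the documents alone is a count: no level term against up to three planned non-zero levels. The power and rejection figures illustrate the remedy; they do not measure the defect, and they depend on assumed effects, correlations and sample sizes. They also treat the outcome as a single number. A whole-waveform SPM threshold is likely to give less power for a localised effect, by an amount that cannot be established because no waveform smoothness is given.

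The documents do not establish a breach of protocol, selective reporting, or that any particular number of levels was run.

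**What to change.** Reconcile protocol sections 1.5 and 5.1 with the SAP, and define PBFR in the SAP by the LOP level or levels actually applied. Then:

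- **If one non-zero level was run:** name it, state that H3 was not tested, and limit conclusions to that level. Cost: about two sentences.
- **If two or more were run:**
  - State how they enter the primary control-versus-PBFR comparisons (each level, one named level, or pooled), and count any added contrasts in the multiplicity adjustment. The number of comparisons behind 0.001 would need to be documented for this.
  - Add a within-participant SPM analysis, within each group, with LOP level as a repeated factor. A workable form is a slope waveform per participant followed by a one-sample SPM t-test.
  - Report BFR versus none separately from the comparison among non-zero levels. State and justify whether the main H3 contrast includes 0%.
  - State the alpha, report estimates with intervals, and label the analysis as added later if it was.

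The second case costs one further SPM analysis per variable and group, on data already collected. Its drawback is limited precision among the non-zero levels, worst at alpha 0.001 or with only two adjacent levels. The report should therefore say that a null trend would not show that restriction level is irrelevant.
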